### **3.4 Study Endpoints**

#### **3.4.1 Primary Study Endpoint**

The primary outcome variable is subjective pain score as assessed by the 10-cm Visual Analog Scale (VAS) up to 72 hours post-operatively as per protocol in the Neurological Intensive Care unit at the Hospital of the University of Pennsylvania. Each pain score will be recorded at 2-hour intervals while the patient is in the ICU, and every 4 hours thereafter, up to 72 hours. Pain scores will only be recorded during waking hours.

#### **3.4.2 Secondary Study Endpoints**

The secondary outcome variables are the subjects' cumulative narcotic requirement, Glasgow Coma Score, the duration of stay in the intensive care unit (ICU), the duration of time in the hospital until discharge, and the duration of time from the end of surgery to the first administration of narcotic analgesic.

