### 1 Introduction

Postoperative pain following craniotomy is a frequent and important cause of distress and hemodynamic instability in the neurosurgical patient population. Current therapeutic options commonly involve the use of systemic intravenous narcotics, which may result in decreased arousal and an inability to complete an adequate neurological examination, an essential component of postoperative care. Targeted cranial blocks with local anesthetic agents have shown to be efficacious in inducing intermediate duration postoperative analgesia. A novel local anesthetic, liposomal bupivacaine, provides up to 72 hours of pain relief in the setting of hemorrhoidectomy, bunionectomy, inguinal hernia repair, total knee arthroplasty and mammoplasty. In this study, we propose to test the investigational agent, liposomal bupivacaine, following craniotomy in a randomized controlled, single-blinded, investigator-initiated study.

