### **3.3 Study Measures**

A 10-cm VAS (where '0' is defined as 'no pain at all' and '10' as 'the worst possible pain' will be used to assess subjects' pain score. This will be assessed every 2 hours after extubation postoperatively while the patient is in the ICU, and every 4 hours after the patient has left the ICU, for 72 hours while inpatient, during waking hours, or until discharge in patients discharged prior to 72 hours post-op.

The Glasgow Coma score (GCS) (Teasdale & Jennett, 1974) will also be assessed at the above time points. Patients with GCS verbal score of <4 will be excluded from statistical analysis because of inability to respond to questions after extubation.

The cumulative doses of narcotics during this time period will also be measured. Intravenous narcotic medications will be given by the nurse taking care of the patient as rescue analgesic, as requested by the patient. If the patient requires more analgesics, the dosage will be increased as needed by the patient following standard clinical guidelines. Nursing personnel will be instructed to administer analgesic according to patient demand. The total rescue analgesic requirement will be noted at the above mentioned time intervals.

The duration of time between the end of the surgical procedure (extubation) and the first administration of rescue narcotic will be recorded.

The total length of ICU stay will be recorded. The total length of hospital stay will also be recorded.

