## **4 Study Population and Duration of Participation**

### **4.1 Duration of Study Participation**

Study participation will last from the intervention (craniotomy) through the patients stay in the hospital. Participation will officially end at the patient's follow-up visit 4-6 weeks postoperatively, at the end of study visit.

We plan to enroll subjects for 12 months (10/2019-10/2020). We expect to enroll 90 neurosurgical patients during that time. Neurosurgical patients will participate in the experiment through the duration of their stay in the hospital. Typically, these stays are 1-2 weeks in duration. Each patient will report his or her VAS pain score (in increments of 1 from a range of 0 - 10) every 2 hours while in the ICU and every 4 hours after leaving the ICU, for a duration of up to 72 hour postoperatively. GCS scores will also be recorded at 2-hour intervals while the patient is in the ICU. The total length of ICU stay will also be recorded. Once the patient is transferred to the neurosurgery ward, GCS will be documented every 4 to 8 hours.

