#### **4.3 Inclusion Criteria**

- $\geq 18$  years of age
- Need for elective supratentorial craniotomy
- Preoperative GCS  $> 13$

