## **6.2 Statistical Methods**

The primary and secondary outcome variables will be examined for group-wise differences with Analysis of Variance statistics. Significant differences in the means will then be subjected to Bonferroni's t-test. Pearson correlation coefficients will be computed for associations between variables. A p-value of <0.05 will be regarded as statistically significant.

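### GCS has no defined per-patient summary and is compared by group means without the patient's own pre-operative score, so the 14-versus-15 starting difference can swamp short post-operative falls

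*Combined protocol and SAP*

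**What the plan says.** GCS is one of five secondary outcomes in section 3.4.2: "The secondary outcome variables are the subjects' cumulative narcotic requirement, Glasgow Coma Score". That section gives no time point, average, minimum, change or event.

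The score is taken many times. Section 3.3 ties it to the pain assessments: "The Glasgow Coma score (GCS) (Teasdale & Jennett, 1974) will also be assessed at the above time points". For pain, the rule is "This will be assessed every 2 hours after extubation postoperatively while the patient is in the ICU", then every 4 hours, in waking hours, up to 72 hours. Section 4.1 agrees for the ICU ("GCS scores will also be recorded at 2-hour intervals while the patient is in the ICU") but differs for the ward: "Once the patient is transferred to the neurosurgery ward, GCS will be documented every 4 to 8 hours".

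Three places bear on the analysis:

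- Section 6.2 applies ANOVA to primary and secondary outcomes and follows up with Bonferroni t-tests: "Significant differences in the means".
- The Study Summary assigns a paired t-test to every secondary endpoint.
- Section 6.2.2 assigns a paired t-test to other outcomes, but its list leaves GCS out.

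Section 4.3 admits only patients with a pre-operative GCS above 13, so each starts at 14 or 15. No analysis section uses that value.

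**The concern.** ANOVA or a t-test needs one number per patient, and the plan does not say which. The patient's mean score is a natural default. On that default, a patient who starts at 14 and stays there differs by a full point from one who starts at 15 and stays there, although neither has changed. A short fall of 2 points moves a patient's mean by much less than that. The comparison can then be dominated by a difference that was there before surgery.

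This matters because wakefulness is part of the trial's rationale. The Introduction says that systemic narcotics "may result in decreased arousal and an inability to complete an adequate neurological examination". A null GCS result from an insensitive comparison could be read as evidence that arousal was equally preserved in all arms.

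**Working it through.** The plan gives no GCS effect size, distribution or power, so there is no figure to reproduce.

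**Inputs from the document.** 90 patients allocated 1:1:1 gives 30 per arm. The 10% dropout in 6.1 leaves 30 × 0.9 = 27. Pre-operative GCS is 14 or 15 (4.3). The most readings possible in 72 hours is 72/2 = 36. Significance is 0.05 (6.2), taken here as two-sided for one pair of arms without multiplicity adjustment.

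**Inputs assumed.** 24 readings per patient; a 2-point fall in 40% of one arm and 10% of the other; the fall lasts *k* readings; a share *p* of patients has a constant pre-operative 14; no scoring noise at first.

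**Step 1: difference in means.** A fall over *k* readings moves that patient's mean by 2*k*/24. The arms differ by (0.40 − 0.10) × 2*k*/24. For *k* = 2: 0.30 × 0.1667 = 0.05 points.

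**Step 2: where the variance comes from.** The starting score contributes *p*(1 − *p*) = 0.2 × 0.8 = 0.16. The falls contribute (2*k*/24)² × (0.4 × 0.6 + 0.1 × 0.9)/2 = 0.0278 × 0.165 = 0.00458. The starting score supplies 0.16/0.16458 = 97%.

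- Raw mean: standardised difference 0.05/√0.16458 = 0.123.
- Change from pre-operative: 0.05/√0.00458 = 0.739.

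**Step 3: power.** Approximately Φ(*d*√(27/2) − 1.96) + Φ(−*d*√(27/2) − 1.96). For 0.123, *d*√13.5 = 0.452 and power is about 7%. For 0.739 it is 2.715 and about 77%. Simulation, which respects the discreteness of the data, gives 8% and 74%.

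For change from pre-operative GCS, *k* cancels: (0.30 × 2*k*/24)/(√0.165 × 2*k*/24) = 0.739 for any *k*. Without noise, averaging the change loses nothing.

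**Step 4: range (simulated power; repeat runs differ by one or two points).**

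| Share at 14 | Fall lasts | Raw mean | Change from pre-operative |
|---|---|---|---|
| 20% | 2 readings | 8% | 74% |
| 5% | 2 readings | 20% | about 74% |
| 20% | 6 readings | 24% | about 74% |
| 20% | 12 readings | 45% | about 74% |
| none | 2 readings | 75% | about 74% |

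**Step 5: other assumptions.** Take 36 readings, 10% versus 50% with a 2-point fall, and 5% of readings one point low by chance. With 20% at 14, the raw mean has about 5%, 10%, 22%, 51% and 80% power for falls of 1, 3, 6, 12 and 24 readings. With all at 15, it runs from 48% to 93%. Mean change has 45–48% for one reading, 86–88% for three and 91–93% for six or more. A fall of 2 or more points (Fisher's test) has 85–88% throughout.

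**Step 6: scoring noise in the Step 1 setting (two-reading fall, 20% at 14).** Let 1%, 2% or 5% of readings be one point low.

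- Mean change keeps 73%, 68% and 60%.
- Fisher's test on any fall goes from 63% to 32%, 17% and 6%. At 5% noise, 1 − 0.95^24 = 71% of patients without a true fall still show one.
- A rank test on lowest minus pre-operative score drops from 74% to 53–58%.
- A fall of 2 or more keeps about 63% at 5% noise. One-point noise cannot create such a fall by itself, so this model favours that count.

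**The case against.** The strongest reply is that the plan never says it averages a patient's scores. That is correct. Section 3.4.2 names only the score, and the means in 6.2 are group means. The power figures therefore describe a likely default, not a stated analysis. What remains is that the summary is undefined and the starting score is unused.

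A reader might infer that averaging hides the effect, so that means should give way to the lowest score. The arithmetic does not support this. With no noise, mean change does as well as the lowest score, and with noise it does better. The loss comes from ignoring the starting value.

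A reader might also infer that the endpoint cannot show a difference. It can: falls that last long, or a population nearly all at 15, are detectable on the raw mean. The documents give neither the 14/15 mix nor the length of falls.

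It could be argued that the paired t-test already pairs each patient with the pre-operative score. The plan does not say so, and such a test would assess change within an arm, not a difference between arms.

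Finally, GCS is not labelled a safety endpoint, and 5.6 has the Safety Officer review it unblinded. Both are true. But those reviews are listed only up to 60 enrolled and state no GCS criterion, so they do not replace the final comparison. Section 4.2 also says the sample size serves secondary outcomes.

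**Conclusion.** The point holds as a gap in specification with a material consequence under plausible conditions. GCS has no per-patient summary, the stated tests conflict, one of them does not fit independent arms, and the pre-operative score is left out. If raw patient means are used, power for the assumed effect lies anywhere from about 8% to 75%, depending on how many patients start at 14 and how long falls last. Using the pre-operative score holds it near 74% without noise, and at 60–73% with 1–5% of readings one point low.

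These figures rest on an assumed effect, reading count and 14/15 mix, and on unadjusted pairwise tests; a Bonferroni correction would lower them. They support the statement that a raw-mean comparison may miss short falls, and nothing stronger. The exclusion of patients with a verbal score below 4 (3.3, 4.4) is a separate matter that also bears on GCS; this change would not resolve it.

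**What to change.** In 3.4.2, define the GCS endpoint as change from the patient's own pre-operative score over the 72-hour window: either the mean change, or the mean score adjusted for pre-operative GCS. State which readings enter, since 3.3 and 4.1 differ on the ward interval. In 6.2, name one comparison between independent arms for this endpoint, and remove the paired t-test for it from the Study Summary.

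Also report, per arm, the number of patients with a fall of 2 or more points from the pre-operative value, with exact confidence intervals. Do not count any fall, because single one-point misreadings would dominate it.

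The lowest score minus pre-operative GCS, compared by a rank test, may be added as a supporting analysis. Its downside is sensitivity to a single mis-scored reading.

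The cost is wording only. Pre-operative GCS must already be known to establish eligibility, and the post-operative scores are already planned.

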## **4 Study Population and Duration of Participation**

### **4.1 Duration of Study Participation**

Study participation will last from the intervention (craniotomy) through the patients stay in the hospital. Participation will officially end at the patient's follow-up visit 4-6 weeks postoperatively, at the end of study visit.

We plan to enroll subjects for 12 months (10/2019-10/2020). We expect to enroll 90 neurosurgical patients during that time. Neurosurgical patients will participate in the experiment through the duration of their stay in the hospital. Typically, these stays are 1-2 weeks in duration. Each patient will report his or her VAS pain score (in increments of 1 from a range of 0 - 10) every 2 hours while in the ICU and every 4 hours after leaving the ICU, for a duration of up to 72 hour postoperatively. GCS scores will also be recorded at 2-hour intervals while the patient is in the ICU. The total length of ICU stay will also be recorded. Once the patient is transferred to the neurosurgery ward, GCS will be documented every 4 to 8 hours.

### **4.2 Total Number of Subjects and Sites**

This project will aim to recruit approximately 7-8 patients per month (90/year) up to a total of approximately 90 patients across the Department of Neurosurgery. This rate of accrual is based on number of potential candidates available from the current case volume for the Department of Neurosurgery at the Hospital of the University of Pennsylvania. No additional recruitment will be required. The duration of the study and the total number of patients listed above are necessary to adequately detect clinically and statistically significant differences in primary and secondary outcomes. The University of Pennsylvania will be the only study site.

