## Study Summary

|                           |   |
|---------------------------|---|
| Title              | Randomized study of cranial blocks for postoperative anesthesia to reduce pain and postoperative opioid usage  |
| Short Title        | Cranial blocks for postoperative anesthesia   |
| IRB Number         | 834603  |
| Protocol Number    | N/A   |
| Methodology        | Prospective single-blinded randomized controlled trial  |
| Study Duration     | 12 months   |
| Study Center(s)    | Single-center   |
| Objectives         | Primary: 

• To assess the effectiveness of analgesia by scalp nerve block with various agents in the first 72 hours following elective craniotomy.

 |
| Number of Subjects | 90  |

|  |   |
|--|---|
| Main Inclusion and Exclusion Criteria | 
Inclusion Criteria
 
 
• <math>\geq 18</math> years of age
 
• Need for elective supratentorial craniotomy
 
• Preoperative GCS <math>> 13</math>
 
 
Exclusion Criteria
 
 
• Preoperative GCS <math>\leq 13</math>
 
• Child (<math>< 18</math> years of age)
 
• Inability to understand or use the visual analog scale (VAS)
 
• Proven or suspected allergy to local anesthetics
 
• Craniotomy incision extending beyond the field of the block
 
• Patients chronically (more than 2 wk) treated with narcotic medications
 
• Previous scalp incision
 
• Bilateral craniotomies
 
• Allergies to local anesthetics
 
• GCS verbal score <math>< 4</math> after extubation
 
• Patients whose surgeries exceed 6 hrs (will be removed from study and maintained with standard of care)
 
• Patients currently on ergot-type oxytotoxic drugs, MAOIs, or certain antidepressants
 
• Lactating mother
 
 |
| Intervention                          | 
This study compares the standard of care to the standard of care plus the administration of bupivacaine or liposomal bupivacaine in patients receiving craniotomies.
   |
| Statistical Methodology               | 
A Mann-Whitney U test will be used to analyze the primary endpoint of subjects' subjective pain scores. A paired t-test will be used for all secondary endpoints.
  |

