### **6.2.2 Analysis of Primary Outcome of Interest**

The Mann-Whitney U test will be used to compare differences in subjective pain scores calculated for patients within 72 hours of surgery. All other outcomes of interest (narcotic usage, ICU length of stay, total length of stay) will be analyzed using a paired t-test.

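### Section 6.2 lets each of five unordered secondary endpoints be called significant at p<0.05, with no error control across endpoints and no link to the primary result

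*Combined protocol and SAP*

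**What the plan says.** Section 3.4.2 gives the secondary endpoints as a plain list: "The secondary outcome variables are the subjects' cumulative narcotic requirement, Glasgow Coma Score, the duration of stay in the intensive care unit (ICU"), then "the duration of time in the hospital until discharge, and the duration of time from the end of surgery to the first administration" of a narcotic. That makes five, with none marked as key and no testing order.

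Section 6.2 treats all outcomes alike: "The primary and secondary outcome variables will be examined for group-wise differences with Analysis of Variance statistics". The follow-up step is "Significant differences in the means will then be subjected to Bonferroni's t-test", and the decision rule is "A p-value of <0.05 will be regarded as statistically significant".

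Two other places give a different secondary analysis. The Study Summary says "A paired t-test will be used for all secondary endpoints", and section 6.2.2 says "All other outcomes of interest (narcotic usage, ICU length of stay, total length of stay) will be analyzed using a paired t-test", which names only three of the five. Neither states an omnibus test or an adjustment.

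Section 4.2 describes the study duration and patient number as "necessary to adequately detect clinically and statistically significant differences in primary and secondary outcomes". The only calculation, in section 6.1, concerns pain scores.

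No section orders the secondary endpoints, adjusts across them, makes them conditional on the primary, or calls them exploratory or supportive.

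**The concern.** Under section 6.2, five endpoints each get their own 5% chance of a false positive. Bonferroni's t-test protects the three arm comparisons inside one endpoint, but it does not know how many endpoints were tested. The chance that at least one of the five is significant by luck is therefore well above 5%.

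This matters here because reduced opioid use stands in the trial's title yet is a secondary endpoint, and sections 10.2 and 10.3 list lower narcotic need and a shorter ICU stay among the possible benefits. The written rule would allow a statistically significant secondary benefit to be reported whatever happened on pain, with nothing in the plan marking it as one of five unprotected tests.

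Replacing the paired t-test with a test for independent groups, or adjusting the primary across arms, would leave this problem in place.

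**Working it through.** **Inputs from the documents.** Five secondary endpoints (3.4.2). Three arms, hence three pairs per endpoint (3.1). Allocation 1:1:1 (3.2). Total 90, so 90/3 = 30 per arm (4.1, 6.1). Dropout 10%, leaving 30 × 0.9 = 27 per arm (6.1). Threshold 0.05 per outcome (6.2).

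**Inputs assumed.** All five secondary null hypotheses true; normal endpoints; one common correlation between endpoints, shown from 0 to 0.9.

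**The plan's own figures.** The documents state no error rate for the secondary family, so there is none to reproduce. The stated sample size of 30 does not reproduce from its inputs. With d = 1.01, two-sided 5% and 80% power, 2 × (1.960 + 0.842)² / 1.01² = 15.4, so 16 per arm (17 with the t distribution), and 17/0.9 = 18.9, so 19 with dropout. This does not affect the present point: the false-positive rate barely depends on arm size, and simulations with 27 and 30 per arm agree.

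**Step 1, independent endpoints.** P(at least one significant ANOVA) = 1 − 0.95⁵ = 1 − 0.774 = 22.6%.

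**Step 2, correlated endpoints.** Simulation of 100,000 trials per setting, 3 arms × 30, with the ANOVA at 5% and then pairwise t-tests at 0.05/3 using the ANOVA error variance:

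| Common correlation | At least one significant ANOVA | At least one named arm difference after ANOVA and Bonferroni |
|---|---|---|
| 0 | 22.5% | 19.3% |
| 0.3 | 21.1% | 18.1% |
| 0.5 | 18.6% | 16.0% |
| 0.7 | 15.3% | 13.3% |
| 0.9 | 10.6% | 9.2% |

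If the Bonferroni t-tests use each pair's own variance instead, the last column runs from 18% to 15% over correlations 0 to 0.5 with 27 per arm. Section 6.2 does not say which variance applies, so the range is given as 15-19%.

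**Step 3, shorter list.** Counting only the three outcomes named in section 6.2.2, 1 − 0.95³ = 14.3% for a significant ANOVA if independent, and 13-14% over correlations 0 to 0.5.

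**Step 4, effect of control.** Each endpoint at 0.05/5 = 0.01 gives 1 − 0.99⁵ = 4.9% if independent, and at most 5 × 0.01 = 5% under any correlation.

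**The case against.** The strongest reply is convention. This is a single-centre, investigator-initiated trial with one primary variable and one stated objective. Secondary endpoints in such trials are often left unadjusted and read as supportive, and no section defines trial success through one of them. That bears on severity, but it does not remove the point. The documents never say the secondary results are supportive, and 6.2 gives them the same significance rule as the primary.

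The size can also be challenged. Some endpoints overlap by construction: ICU stay is part of hospital stay, and cumulative narcotic use begins with the first dose. GCS is restricted by the entry criteria and by the exclusion for low verbal scores, and the other endpoints are durations or totals, so normality is a simplification. The overlap argues for the lower rows of the table. Non-normality matters less: Step 1 needs only that each test holds its 5% level, although a very coarse GCS distribution could depart from it.

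Three stronger readings are tempting but not supported:

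- **A 40-48% error rate.** Three unadjusted pairwise tests on each endpoint would give 48% to 40% at correlations 0 to 0.5. No section prescribes that. The Study Summary and 6.2.2 name a paired t-test without contrasts, while 6.2 requires ANOVA and then Bonferroni. Much of that figure comes from comparing arms within an endpoint (about 12% for one endpoint alone, against 5% for its ANOVA). It belongs to the conflict over the test, which must be reconciled separately.
- **Section 4.2 as a decision rule.** It is a justification of sample size. It shows that significance on secondary outcomes is intended; the rule itself is in 6.2.
- **A promise of shorter stays, or a plan to present a failed primary as a success.** Section 10.2 speaks only of potential benefit, and the documents do not predict how results will be reported. What can be said is that the written rule does not prevent it.

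**Conclusion.** The concern holds for the procedure in section 6.2. Five unordered endpoints may each be declared significant at 0.05, with no control across them and no dependence on the primary. With all five nulls true and correlations of 0 to 0.5, the chance of at least one false secondary finding is about 19-23% counting a significant ANOVA, or 15-19% counting a named arm difference. At correlations of 0.7 to 0.9 the ANOVA figure is about 11-15%. It would reach 5% only if the endpoints were in effect one endpoint.

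The correlations are assumptions, and the figures describe the case in which no secondary effect exists. The primary analysis is not affected. This should be corrected because the rule is explicit and the repair costs little, but it does not invalidate the trial.

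**What to change.** In sections 3.4.2 and 6.2, name cumulative narcotic requirement, the opioid outcome in the title, as the single key secondary. Test it at 5% only if the primary is significant, using the same pre-named arm contrast or contrasts and the same between-arm adjustment as the primary. If several contrasts are named, open the gate contrast by contrast: a contrast is tested on narcotic requirement only if that contrast succeeded on pain, and at the same share of the 5%. Report GCS, ICU stay, hospital stay and time to first narcotic as estimates with 95% confidence intervals and no significance claim.

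If the investigators prefer to keep all five as formal tests, apply Holm across endpoints with between-arm control inside each. The simplest valid form runs Holm over all endpoint-by-contrast p-values together. With one contrast the smallest p-value faces 0.05/5 = 0.01; with three contrasts it faces 0.05/15 = 0.0033.

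In either case, align the wording of sections 4.2 and 6.2, and reconcile the Study Summary and 6.2.2 with 6.2 so that the rule has one test to act on.

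The cost is wording only, with no added patients, visits or data. The downside is that four endpoints can no longer be called significant or, under Holm, that all five face stricter thresholds.
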